8 INVESTIGATIONAL PRODUCT

8.1 Manufacturing and Storage

The investigational product will be provided to Prism Clinical by the Sponsor. The investigational product will be carefully stored at the study site in a lockable, limited access area, accessible only to study team personnel in compliance with pertinent regulations. Only authorized persons will have access to the investigational product. In an ambient condition the product will be stored at room temperature and will not be exposed to direct sunlight or heat. The product and placebo will be provided in single use sachet, both blinded in label. The investigational products will be kept in a locked investigational product storage room at Prism Clinical on receipt. An accountability log will be kept for the investigational products.

All unused investigational product will be returned to the study sponsor by Prism Clinical (at the sponsor's expense) or destroyed on receipt of written confirmation from the sponsor at study closeout (within one month of last participant visit).

Manufactured by:

Bioenergy Life Science, Inc.

8.2 Labelling and Coding

The investigational product will be labeled according to the requirements of ICH-GCP guidelines and applicable local regulatory guidelines. Investigational product will be randomized and coded by an unblinded person at KGK Science Inc. who is not involved in data collection or analysis.

8.3 Investigational Product (RiaGevTM)

Dietary Ingredient	Quantity (2 g/sachet, in 3 capsules)
Bioenergy Ribose® (D-ribose)	1280mg
Vitamin B3 (Nicotinamide)	240mg

Non-medical ingredients: 480mg Palm oil

8.4 Comparator

Ingredients: 480mg Palm oil and 1280mg Dextrose, packaged in 3 capsules in a sachet

8.5 Directions

Participants will be instructed to take two doses of the IP daily, once in the morning and once in the evening. Each dose will be 3 capsules, one dose will be administered immediately before breakfast and the other dose will be administered immediately before dinner. In both study periods, on day 1 only the evening dose will be administered and on day 8 only morning dose will be administered. The Clinic staff will instruct participants to save all unused and open packages and return them to Prism Clinical for a

determination of compliance. If a dose is missed participants are instructed to consume the missed dose anytime on the same day, except at bedtime. Participants will be advised not to exceed two servings daily.

8.6 Randomization

A randomization schedule will be created and provided to the Investigator indicating the order of randomization. Each participant will be assigned a randomization code according to the order of the randomization list generated using www.randomization.com. Enrolled participants will be randomized to the different treatment arms at day 1 in a double-blind manner.

8.7 Unblinding and Allocation Concealment

Unblinding should not occur except in the case of emergency situations. In the event that a serious adverse event occurs, for which the identity of the investigational product administered is necessary to manage the participant's condition, the treatment received by the participant will be unblinded and the investigational product identified. Concealment of the allocation of treatment will be employed through the use of opaque sealed envelopes, each labeled with a randomization number. Each envelope will contain information regarding the treatment associated with each randomization number. These envelopes will be readily available for the investigator to open in the event that it becomes necessary to know which product a participant is taking for the sake of the participant health care. The sponsor must be notified of any unblinding within 24 hours. Details of participants who are unblinded during the study will be included in the Final Report.

9 STUDY ASSESSMENTS

* At the discretion of the Qualified Investigator, any participants falling outside of the screening window (Day -45 to Day -1) due to scheduling issues will be asked to repeat eligibility/screening procedures prior to randomization at baseline.

9.1 Visit 1 – Screening (Day -45 to Day -14) *

Participants will show up at the clinic in a fasted state (8h) for visit 1. At screening, an informed consent form will be given to the potential volunteer. They will be required to read the information and will be given the opportunity to seek more information if needed, or provided with the option of taking the consent form home to review prior to making their decision. If agreeable, the volunteer will sign the consent form and receive a duplicate of the signed copy. Once consent has been obtained, the screening visit will proceed. Each volunteer will be sequentially assigned a screening number to be entered in the screening and enrollment log.

Screening assessments include:

- 1. Review medical history, concomitant therapies and current health status
- 2. Assess inclusion and exclusion criteria
- 3. Urine pregnancy test for female potential participants that are of child-bearing potential
- 4. Seated resting blood pressure and heart rate measurements
- 5. Weight and height measurements (BMI calculation)
- 6. Physical exam
- 7. EKG
- 8. Collect fasted blood samples for the analysis of Complete Blood Count (CBC), HbA1c, electrolytes (Na, K, Cl), fasting glucose, eGFR, creatinine, AST, ALT, and total bilirubin
- 9. Complete maximum heart rate treadmill test (Section 9.12.6)
- 10. Dispense 3-Day Food Record and sleep diary
- 11. Dispense salivary collection kit and instruct participants on use (Section 9.12.5)

The next visit will be scheduled for potentially eligible participants for baseline (Day 1).

Reminders for participants prior to their next in-clinic visit:

- 1. Abide by instructions for medications as per Section 7.3.1 and OTC medications, supplements, and food/drinks as per Section 7.3.2
- 2. Complete and return the Food record for the three days prior to baseline visit for review
- 3. Maintain current level of physical activity and maintain and record sleep schedule in diary
- 4. Participants will be advised follow the dietary guidelines (see appendix 15.3)
- 5. Participants will collect baseline salivary cortisol the morning of their Baseline Visit (Section 9.12.5)

9.2 Run-in period – 2 weeks (Day -13 to Day 0)

Participants will undergo a 14 days run-in period.

Participants are reminded to follow the dietary guidelines 15.3, avoid the consumption of the medications and supplements as per 7.3.1 and 7.3.2, collect saliva the morning of the next in-clinic visit, maintain current level of physical activity and maintain and record sleep schedule.

9.3 Visit 2 - Baseline (period 1- Day 1+1 Day)

Eligible participants will return to the clinic fasted (8h) with completed saliva kit, sleep diary and food diary for baseline assessments.

Baseline (Day 1) assessments include:

- 1. Return completed salivary cortisol collection kit
- 2. Review concomitant therapies
- 3. Assess inclusion and exclusion criteria
- 4. Urine pregnancy test for female potential participants that are of child-bearing potential
- 5. Seated resting blood pressure and heart rate measurements
- 6. Review AEs
- 7. Weight measurements (BMI calculation)
- 8. Physical exam
- 9. Randomization of eligible participants
- 10. Collect Food Record and sleep diary for review
- 11. Collect blood sample at T=0 (pre-meal) for fasting serum glucose, insulin
- 12. Standardized meal provided (see Appendix 15.2)
- 13. Collect post-meal blood sample for serum glucose and insulin analysis at:
 - a. T=15min
 - b. T= 30min
 - c. T=45min
 - d. T=60min
 - e. T=90min
 - f. T= 2hrs
- 14. Collect blood sample at T=2 hours (post-meal) for NAD+
- 15. (Optional) Measure NADH with skin fluorescence
- 16. Complete treadmill exercise protocol (Section 9.12.7)
- 17. (Optional) Measure NADH with skin fluorescence
- 18. Collect blood sample for GSH/GSSG and ATP/AMP analysis
- 19. Administer CIS questionnaire
- 20. Dispense investigational product and instruct participants on use. Participants will be instructed to take their first dose of the investigational product in evening of Day 1.
- 21. Dispense saliva collection kit
- 22. Dispense 7-Day Food Record and subject sleep and treatment diary

The next visit will be scheduled for visit 3 (period 1- Day 3)

Reminders for participants prior to their next in-clinic visit:

- 1. Abide by instructions for medications as per Section 7.3.1 and OTC medications, supplements, and food/drinks as per Section 7.3.2
- 2. Maintain current level of physical activity and sleep schedule

- 3. Complete and return the food record, sleep and treatment diary
- 4. Participants will be advised to follow the dietary guidelines (see appendix 15.3)
- 5. Collect saliva in the morning 15 minutes after waking and prior to consumption of food
- 6. Return to clinic one hour after consuming investigational product/placebo and breakfast on the next visit day

9.4 Visit 3 - (period 1- Day 3+1 Day)

Participants will return to the clinic one hour after consuming investigational product/placebo for Visit 3 assessments with unused investigational product, completed Subject sleep and treatment diary, saliva kit and food records.

Visit 3 assessments include:

- 1. Review concomitant therapies
- 2. Seated resting blood pressure and heart rate measurements
- 3. Weight measurements (BMI calculation)
- 4. Return unused investigational product in the original packaging and remnants and calculate compliance by counting the returned unused investigational product
- 5. Return saliva collection kit
- 6. Review AEs
- 7. Collect food record and subject sleep and treatment diary for review
- 8. Collect blood sample for NAD+ analysis
- 9. Administer CIS questionnaire
- 10. Re-dispense 7-Day Food Record
- 11. Dispense Subject sleep and treatment Diary
- 12. Dispense new saliva collection kit
- 13. Dispense new investigational product and instruct participants on use

The next visit will be scheduled for visit 4 (period 1- Day 5)

Reminders for participants prior to their next in-clinic visit:

- 1. Abide by instructions for medications as per Section 7.3.1 and OTC medications, supplements, and food/drinks as per Section 7.3.2
- 2. Maintain current level of physical activity and sleep schedule
- 3. Complete and return the food record and sleep and treatment diary
- 4. Participants will be advised to follow the dietary guideline (see Appendix 15.3)
- 5. Collect saliva in the morning 15 minutes after waking and prior to consumption of food
- 6. Return to clinic one hour after consuming investigational product/placebo and breakfast on the next visit day

9.5 Visit 4 – (period 1- Day 5+1 Day)

Participants will return to the clinic one hour after consuming investigational product/placebo for Visit 4 assessments with unused investigational product, completed Subject sleep and treatment diary, saliva kit and food records.

October 4th, 2019 -Confidential- Page **24** of **52**

Visit 4 assessments include:

- 1. Review concomitant therapies
- 2. Seated resting blood pressure and heart rate measurements
- 3. Weight measurements (BMI calculation)
- 4. Return unused investigational product in the original packaging and remnants and calculate compliance by counting the returned unused investigational product
- 5. Return saliva collection kit
- 6. Review AEs
- 7. Collect food record and subject sleep and treatment diary for review
- 8. Collect blood sample for NAD+ analysis
- 9. Administer CIS questionnaire
- 10. Re-dispense 7-Day Food Record
- 11. Dispense Subject sleep and treatment Diary
- 12. Dispense saliva collection kit
- 13. Dispense new investigational product and instruct participants on use

The next visit will be scheduled for visit 5 (period 1- Day 8)

Reminders for participants prior to their next in-clinic visit:

- 1. Abide by instructions for medications as per Section 7.3.1 and OTC medications, supplements, and food/drinks as per Section 7.3.2
- 2. Maintain current level of physical activity and sleep schedule
- 3. Complete and return the food record and sleep and treatment diary
- 4. Participants will be advised to follow the dietary guideline (see appendix 15.3)
- 5. Collect saliva in the morning 15 minutes after waking and prior to consumption of food
- 6. Return to clinic in a fasting state (8h), without taking IP on the next visit day

9.6 Visit 5 - (period 1- Day 8+1 Day)

Participants will return to the clinic fasted (8h) for Visit 5 assessments with unused investigational product, completed Subject sleep and treatment diary, saliva kit, and food records.

Visit 5 (Day 6) assessments include:

- 1. Review concomitant therapies
- 2. Seated resting blood pressure and heart rate measurements
- 3. Weight measurements (BMI calculation)
- 4. Return unused investigational product in the original packaging and remnants and calculate compliance by counting the returned unused investigational product
- 5. Return saliva collection kit
- 6. Review AEs
- 7. Collect Food Record and Subject sleep and treatment diary for review
- 8. Collect blood sample at T=0 (pre-meal) for fasting serum glucose, insulin, CBC, electrolytes (Na, K, Cl), eGFR, creatinine, AST, ALT, total bilirubin
- 9. Administer the investigational product
- 10. Standardized meal provided (see Appendix 15.2)
- 11. Collect post-meal blood sample for serum glucose and insulin analysis at:
 - a. $T = \overline{15}$ min

A randomized, double-blind, comparator-controlled, cross-over study to investigate the safety and efficacy of RiaGev[™] in healthy adults

- b. T=30min
- c. T=45min
- d. T=60min
- e. T=90min
- f. T=2 hours
- 12. Collect blood sample at T=2 hours (post-meal) for NAD+
- 13. (Optional) Measure NADH with skin fluorescence
- 14. Complete treadmill exercise protocol (Section 9.12.7)
- 15. (Optional) Measure NADH with skin fluorescence
- 16. Collect blood sample for GSH/GSSG and ATP/AMP
- 17. Administer CIS questionnaire
- 18. Dispense 7-Day Food Record and Subject sleep and treatment Diary
- 19. Dispense saliva collection kit

The next visit will be scheduled for visit 6 (period 2- Day 1)

Reminders for participants prior to their next in-clinic visit:

- 1. Abide by instructions for medications as per Section 7.3.1 and OTC medications, supplements, and food/drinks as per Section 7.3.2
- 2. Maintain current level of physical activity and sleep schedule
- 3. Complete the food record for three days before next study visit and return the food record and sleep and treatment diary
- 4. Participants will be advised to follow the dietary guideline (see appendix 15.3)
- 5. Participants will collect baseline salivary cortisol the morning of their Baseline Visit (Section 9.12.5)

9.7 Washout period (Day 9 to Day 15+3 Days)

Participants will undergo a 7-day washout prior to visit 6.

Participants are reminded to follow the dietary guidelines 15.3, avoid the consumption of the medications and supplements as per 7.3.1 and 7.3.2, collect saliva the morning of the next in-clinic visit, and maintain current level of physical activity and maintain and record sleep schedule.

9.8 Visit 6 – Baseline (period 2- Day 1+1 Day)

Participants will return to the clinic fasted (8h) for Visit 6 assessments with completed Subject sleep and treatment diary, saliva kit and food records.

Visit 6 (Day 1) assessments include:

- 1. Review concomitant therapies
- 2. Seated resting blood pressure and heart rate measurements
- 3. Weight measurements (BMI calculation)
- 4. Collect Food Record and Subject sleep and treatment diary for review

- 5. Return saliva collection kit
- 6. Review AEs
- 7. Collect blood sample at T=0 (pre-meal) for fasting serum glucose, insulin, CBC, electrolytes (Na, K, Cl), eGFR, creatinine, AST, ALT, total bilirubin
- 8. Standardized meal provided (see Appendix 15.2)
- 9. Collect post-meal blood sample for serum glucose and insulin analysis at:
 - a. T=15min
 - b. T= 30min
 - c. T=45min
 - d. T=60min
 - e. T=90min
 - f. T=2hrs
- 10. Collect blood sample at T=2 hours (post-meal) for NAD+
- 11. (Optional) Measure NADH with skin fluorescence
- 12. Complete treadmill exercise protocol (Section 9.12.7)
- 13. (Optional) Measure NADH with skin fluorescence
- 14. Collect blood sample for GSH/GSSG and ATP/AMP analysis
- 15. Administer CIS questionnaire
- 16. Dispense 7-Day Food Record and subject sleep and treatment diary
- 17. Dispense saliva collection kit
- 18. Dispense new investigational product and instruct participants on use

The next visit will be scheduled for visit 7 (period 2- Day 3)

Reminders for participants prior to their next in-clinic visit:

- 1. Abide by instructions for medications as per Section 7.3.1 and OTC medications, supplements, and food/drinks as per Section 7.3.2
- 2. Maintain current level of physical activity and sleep schedule
- 3. Collect saliva in the morning 15 minutes after waking and prior to consumption of food
- 4. Complete and return the food record and sleep and treatment diary
- 5. Participants will be advised to follow the dietary guideline (see appendix 15.3)
- 6. Return to clinic one hour after consuming investigational product/placebo on the next visit day

9.9 Visit 7 - (period 2- Day 3+1 Day)

Participants will return to the clinic for Visit 7 assessments one hour after consuming investigational product/placebo with unused investigational product, completed Subject sleep and treatment diary, saliva kit and food records.

Visit 7 assessments include:

- 1. Review concomitant therapies
- 2. Seated resting blood pressure and heart rate measurements
- 3. Weight measurements (BMI calculation)
- 4. Return unused investigational product in the original packaging and remnants and calculate compliance by counting the returned unused investigational product
- 5. Return saliva collection kit

- 6. Review AEs
- 7. Collect food record and subject sleep and treatment diary for review
- 8. Collect blood sample for NAD+ analysis
- 9. Administer CIS questionnaire
- 10. Re-dispense 7-Day Food Record
- 11. Dispense Subject sleep and treatment diary
- 12. Dispense saliva collection kit
- 13. Dispense new investigational product and instruct participants on use

The next visit will be scheduled for visit 8 (period 2- Day 5)

Reminders for participants prior to their next in-clinic visit:

- 1. Abide by instructions for medications as per Section 7.3.1 and OTC medications, supplements, and food/drinks as per Section 7.3.2
- 2. Maintain current level of physical activity and sleep schedule
- 3. Collect saliva in the morning 15 minutes after waking and prior to consumption of food
- 4. Complete and return the food record and sleep and treatment diary
- 5. Participants will be advised to follow the dietary guideline (see appendix 15.3)
- 6. Return to clinic one hour after consuming investigational product/placebo on the next visit day

9.10 Visit 8 - (period 2- Day 5+1 Day)

Participants will return to the clinic for Visit 8 assessments one hour after consuming investigational product/placebo with unused investigational product, completed Subject sleep and treatment diary, saliva kit, and food records.

Visit 8 assessments include:

- 1. Review concomitant therapies
- 2. Seated resting blood pressure and heart rate measurements
- 3. Weight measurements (BMI calculation)
- 4. Return unused investigational product in the original packaging and remnants and calculate compliance by counting the returned unused investigational product
- 5. Return saliva collection kit
- 6. Review AEs
- 7. Collect food record and subject sleep and treatment diary for review
- 8. Collect blood sample for NAD+ analysis
- 9. Administer CIS questionnaire
- 10. Re-dispense 7-Day Food Record
- 11. Dispense Subject sleep and treatment diary
- 12. Dispense saliva kit
- 13. Dispense new investigational product and instruct participants on use

The next visit will be scheduled for visit 9 (period 2- Day 8)

Reminders for participants prior to their next in-clinic visit:

1. Abide by instructions for medications as per Section 7.3.1 and OTC medications, supplements, and food/drinks as per Section 7.3.2

- 2. Maintain current level of physical activity and sleep schedule
- 3. Collect saliva in the morning 15 minutes after waking and prior to consumption of food
- 4. Complete and return the food record and sleep and treatment diary
- 5. Participants will be advised to follow the dietary guideline (see appendix 15.3)
- 6. Return to clinic in a fasting state (8h), without taking IP on the next visit day

9.11 Visit 9 – End of the Study (period 2- Day 8+1 Day)

Participants will return to the clinic fasted (8h) for Visit 9 assessments with unused investigational product, completed Subject sleep and treatment diary, saliva kit, and food records.

Visit 9 assessments include:

- 1. Review concomitant therapies
- 2. Seated resting blood pressure and heart rate measurements
- 3. Weight measurements (BMI calculation)
- 4. Return unused investigational product in the original packaging and remnants and calculate compliance by counting the returned unused investigational product
- 5. Physical Exam
- 6. Collect Food Record and Subject sleep and treatment diary for review
- 7. Return saliva collection kit
- 8. Review AEs
- 9. Collect blood sample at T=0 (pre-meal) for fasting serum glucose, insulin, Complete Blood Count (CBC), electrolytes (Na, K, Cl), eGFR, creatinine, AST, ALT, total bilirubin
- 10. Administer the investigational product
- 11. Standardized meal provided (see appendix 15.2)
- 12. Collect post-meal blood sample for serum glucose and insulin analysis at:
 - a. T=15min
 - b. T= 30min
 - c. T=45min
 - d. T=60min
 - e. T=90min
 - f. T=2hrs
- 13. Collect blood sample at T=2 hours (post-meal) for NAD+
- 14. (Optional) Measure NADH with skin fluorescence
- 15. Complete treadmill exercise protocol (Section 9.12.7)
- 16. (Optional) Measure NADH with skin fluorescence
- 17. Collect blood sample for GSH/GSSG and ATP/AMP Analyses
- 18. Administer CIS questionnaire

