10 SAFETY INSTRUCTIONS AND GUIDANCE

10.1 Adverse Events and Laboratory Abnormalities

10.1.1 Adverse Events

An adverse event (AE) is any untoward medical occurrence in a clinical investigation participant who has been administered an investigational product and does not necessarily have a causal relationship with this treatment. An AE can be any unfavorable and unintended sign (including an abnormal laboratory finding), symptom, or disease temporally associated with the use of a product, whether or not it is considered related to that product. Pre-existing conditions that worsen during a study are to be reported as AEs.

During the study, participants should record any adverse effects in their diary. At each visit the participant will be asked, "Have you experienced any difficulties or problems since I saw you last?". Any adverse events (AEs) will be documented in the study record and will be classified according to the description, duration, intensity, frequency, and outcome. The qualified investigator will assess any AEs and decide causality.

Intensity of AEs will be graded on a three-point scale (mild, moderate, severe) and reported in detail in the study record.

Mild: Awareness of event but easily tolerated

Moderate: Discomfort enough to cause some interference with usual activity

Severe: Inability to carry out usual activity

The causality relationship of investigational product to the adverse event will be assessed by the qualified investigator as either:

Most probable: There is a reasonable relationship between the investigational product and AEs.

The event responds to withdrawal of investigational product (dechallenge) and

recurs with rechallenge when clinically feasible.

Probable: There is a reasonable relationship between the investigational product and AEs.

The event responds to dechallenge.

Possible: There is a reasonable relationship between the investigational product and AEs.

Dechallenge information is lacking or unclear.

Unlikely: There is a temporal relationship to the investigational product administration but

there is no reasonable causal relationship between the investigational product and

the AEs.

Not related: There is no temporal relationship to investigational product administration or

there is a reasonable causal relationship between non-investigational product,

concurrent disease or circumstance and the AEs.

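### No adverse event collection is scheduled after the last Period 2 dose, so the scheduled AE window is about 7 days in Period 2 against about 15 in Period 1

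*Protocol*

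**What the plan says.** Protocol 9.11 covers Visit 9, which is Day 8 of Period 2 and the end of the study. Its list has 18 items. The diary is handed in at item 6 ("6. Collect Food Record and Subject sleep and treatment diary for review") and AEs are reviewed once, at item 8. After that come the fasting draw (item 9), the dose ("10. Administer the investigational product"), the meal (11), six timed post-meal draws (12), the two-hour NAD+ sample (13), the treadmill (15), the last draw ("17. Collect blood sample for GSH/GSSG and ATP/AMP Analyses") and the CIS questionnaire (18). Section 8.5 states that "on day 8 only morning dose will be administered", so item 10 is the final dose of the second product.

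Section 10.1.1 names two routes for AEs. One is the diary ("During the study, participants should record any adverse effects in their diary"). The other is an open question at each visit about problems since the previous contact. The same section says that any AE will be documented and gives no end date. Section 10.2.1 deals with following up AEs already identified. The schedules in protocol 1.3, Appendix 15.1 and SAP Table 2 all stop at Visit 9 and show no diary dispensed there.

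Visit 5 (9.6) has the same order, with AE review at item 6 and the dose at item 9. A new diary is then dispensed at item 18. Section 9.7 says "Participants will undergo a 7-day washout prior to visit 6", and at Visit 6 (9.8) the diary is collected (item 4) and AEs are reviewed (item 6).

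AE incidence is the first safety outcome in protocol section 5 and SAP 1.5. SAP 2.3.1 tabulates AEs by study group and tests the proportion of participants with at least one. Neither protocol 11.3.2 nor SAP 2.3.1 defines an AE window or says to which product an event during washout belongs.

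**The concern.** At Visit 9 both named AE routes are listed before the final dose. A participant who becomes unwell after that dose, on the treadmill or after going home is not asked about it at any planned point. The Visit 9 safety bloods are also drawn after the only AE question. Section 10.1.4 makes accompanying symptoms one ground for recording an abnormal result as an AE, and no later contact is scheduled at which to ask about symptoms.

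The same event after the last dose of Period 1 would be picked up at Visit 6. Whether a late event is counted thus depends on the period in which the product was taken. The resulting counts feed a table and a significance test by product, and safety is half of the stated study objective.

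**Working it through.** The plan gives no figure of its own on this point, so the check is a count of doses and days. All days are nominal visit days.

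**Doses per period** (8.5: two a day, evening only on Day 1, morning only on Day 8)
- Day 1: 1. Days 2 to 7: 6 × 2 = 12. Day 8: 1. Total: 1 + 12 + 1 = 14.
- Taken before the Visit 9 AE review: 13 of 14 (93%). The remaining dose is 1/14 = 7%.

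**Scheduled AE cover after the last dose**

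| | Period 1 | Period 2 |
|---|---|---|
| AE review on Day 8 | 9.6 item 6, before dose (item 9) | 9.11 item 8, before dose (item 10) |
| New diary that day | yes (9.6 item 18) | no |
| Next AE review | Visit 6 (9.8 item 6) | none |
| Doses followed by an AE review | 14 of 14 | 13 of 14 |

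**Length of the window**
- Washout is Days 9 to 15, so Visit 6 falls on about Day 16. From Day 8 that is 16 − 8 = 8 days, or 8 + 3 + 1 = 12 with the washout and Visit 6 allowances.
- First dose to last AE review in Period 1: Day 1 to Day 16, 16 − 1 = about 15 days.
- First dose to last AE review in Period 2: Day 1 to Day 8, 8 − 1 = about 7 days.

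**Visit 9 activity after the AE review**
- Blood draws: T = 0, 15, 30, 45, 60, 90 and 120 minutes, plus one after exercise. That is 8 of 8 time points.
- Listed time in clinic after the dose: about 2 hours, then up to 5 + 30 = 35 minutes on the treadmill (9.12.7).

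**Who is affected**
- With 18 participants and two periods there are 36 participant-periods. Up to 18 of them, all in Period 2, lack cover after the last dose.
- With 9 per sequence, that is 9 on each product. If there is no dropout and washout events go to the preceding product, each product has 9 × 15 + 9 × 7 = 135 + 63 = 198 scheduled participant-days. The two totals are equal.

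**The case against.** The case for leaving the plan alone has four parts.

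First, the list need not be a strict sequence. In 9.1, eligibility is assessed at item 2, before the tests that decide it, and the schedule marks AEs at Visit 1 although 9.1 has no AE item. This stands in part. The timed items are ordered, but the place of the AE review within Visit 9 is an inference. The absence of any contact after discharge does not depend on it.

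Second, a reader might infer that events after the last dose are never collected. The documents do not support that. Section 10.1.1 requires any AE to be documented, SAE classification under 10.3 runs from notification, and the participant remains with staff for roughly 2.5 hours after the dose. What is missing is scheduled or solicited collection; only events after discharge have no planned route.

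Third, a reader might infer a bias for or against RiaGev. The 9:9 allocation puts each product in Period 2 equally often, so the comparator loses the same window in the same number of people. Unequal dropout between sequences could disturb this (11.1 allows 20% loss, and 7.4 rules out replacement), but the design does not build it in.

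Fourth, the safety outcome concerns events while supplemented, 13 of 14 doses precede the question, and the Visit 5 to Visit 6 gap is a washout rather than planned AE follow-up. This is fair, and it means that matching that gap after Visit 9 is one option rather than a necessity. It does not explain why the 14th dose is covered in one period and not in the other.

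**Conclusion.** The gap is real and modest. As written, one dose in 14 and all time after it lack scheduled AE collection in Period 2, and the scheduled window is about 7 days against about 15 in Period 1. Up to 18 of 36 participant-periods are affected, equally split between products. The consequence is under-ascertainment and a window that differs by period, with no rule for assigning washout events. The window figures rest on nominal visit days, and the in-clinic part of the gap rests on reading 9.11 in its listed order. The documents give no event rate from which to estimate how many AEs would be missed.

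**What to change.** 1. Make an AE review the last item of 9.11, after the dose, treadmill and final draw, and do the same in 9.6.
2. In protocol 11.3.2 and SAP 2.3.1, define one AE window that is the same for both periods, and state how washout events are assigned to a product. There are two ways to do this:
   - close the window at the end of the Day 8 visit in both periods for the between-product comparison, listing later events separately; or
   - add one brief AE telephone contact after Visit 9, at an interval matching the Visit 5 to Visit 6 gap.

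The cost is one extra question at each of two visits. If the call is chosen, add one short contact for each of 18 participants and about a week's delay to last participant out. Closing the window needs no extra contact, but it leaves events after discharge from Visit 9 unsolicited.
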